Yoga is a highly popular practice, which is increasingly being leveraged as a part of Veterans' PTSD recovery programs. Although initial evidence suggests the usefulness of this strategy, it is urgent that we gather more evidence as to its efficacy for Veterans and understand its mechanisms of action. Such information is critical if we are to find ways to replicably deliver yoga to Veterans for symptom management. By focusing on key mechanistic variables that are linked to the development and maintenance of PTSD and are impacted by yoga, we believe that we will be able to identify pathways to change. This information, in turn, can be used to optimize practice and create delivery guidelines. This project therefore represents an important next step in yoga intervention research.

Preliminary Studies and Current Status of the Field

We relied on three primary sources of preliminary information in designing the proposed study: clinical data from ongoing yoga groups at a VA San Diego, ongoing and past studies at our facility of yoga and other complementary interventions, and extant literature on yoga for PTSD.

Acceptability

Clinical data supports the acceptability of yoga for PTSD among Veterans at this facility. There has been a “Yoga, Nutrition and Meditation” group for “pain and suffering” at the Oceanside Community Based Outpatient Clinic since 2015. Offered in 8-week group meetings, the group features gentle hatha yoga with some adaptations for physical limitations (e.g., availability of seated poses). In FY 16, 66 unique Veterans took advantage of this offering, accounting for 330 visits. In FY17 to date, there have been 53 unique participants with a total of 294 encounters. Thus, patients on average are completing 5-6 of the 8 sessions.

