Mechanisms of change: Coping model. Again, we hope to identify a latent variable indicating maladaptive coping strategies that are associated with PTSD through use of a set of indicators. The **Ruminative Thought Style Questionnaire (RTSQ)** is a 20-item, Likert-based (1-7) scale with good psychometric properties (Cronbach's α .92, strong correlations with measures of depression, anxiety and repetitive thought) and demonstrated separability from mood (Brinker & Dozois, 2009). The **Emotion Regulation Questionnaire (ERQ;** Gross & John, 2003) is a 10-item measure of reappraisal and expressive suppression, which are thought to be effective and ineffective emotion regulation strategies respectively. The ERQ expressive suppression subscale has previously been shown to be impacted by yoga in PTSD patients (Dick et al., 2014) and has good convergent and discriminant validity and internal consistency (Gross & John, 2003). Experiential avoidance will be quantified using the **Brief Experiential Avoidance Questionnaire (BEAQ;** Gamez et al., 2014). This 15-item Likert-based (1-6) measure was developed to improve on the Acceptance and Action Questionnaire – II (AAQ-II), which has been shown to be highly reflective of general distress (Wolgast, 2014). The BEAQ has good internal consistency (Cronbach's α .86) and is more strongly related to measures of avoidance than negative affect.

To assess the construct of tolerance of discomfort, we will use the **Distress Tolerance Scale (DTS),** a 15-item, Likert-based (1-5) scale with good internal consistency (Cronbach's α .75) and test-retest reliability ($r = .61$). The DTS has been shown to be associated with PTSD (Vujanovic et al., 2013), prospectively predict problematic alcohol use (Simons & Gaher, 2005) and be modified by hatha yoga (Medina et al., 2015).

Assessment schedule. The assessment schedule presented in Table 1 is designed to balance depth of understanding with participant burden. Constructs with a greater degree of fluctuation (e.g., mental health symptoms) are administered more frequently, whereas those that change more slowly are assessed less frequently (e.g., functioning).

Table 1: Summary of Assessments

	Instrument	Aim	Baseline	Weekly	Mid-treatment	Post-treatment	Follow-up	Assessment session
Descriptives, Eligibility, Covariates	Demographics		X					1
	Veterans Specific Activity Questionnaire		X					1
	Alcohol Use Disorders Identification Test		X	X	X	X	X	1
	Life Events Checklist		X					1

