Hypotheses 2a.1, 2a.2, 2b.1 and 2b.2 initially will be tested using the same mixed model procedure identified in Hypothesis 1a and 1b. To test for mediation effect, we will utilize the analytic strategy described by Krull and MacKinnon (1999, 2001). In this approach, four conditions must be met: a) a significant relationship between the independent variable (treatment) and the dependent variable (PTSD symptoms as measured by CAPS), b) a significant relationship between the independent variable and the proposed mediator (Attention Model: mindfulness and attentional control; Coping Model: tolerance of discomfort and coping), c) a significant relationship between the mediators and the outcome, and d) the relationship between the independent variable and outcome must be significantly lower after controlling for the proposed mediator. The multiple-mediation model includes a multiple-path mediating effect through both mediators (i.e. mindfulness and attentional control or tolerance of discomfort and maladaptive coping), which allows one mediator (e.g., mindfulness) to causally affect the other mediator (e.g., attentional control). Multimodal assessment is used for Attentional Control, Tolerance of Discomfort and Coping based on the theoretical models discussed previously. The relation among these variables and their individual contribution to the construct of interest will be examined in order to

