remove variables or create composites. Correlation coefficients among the outcomes for each mediator will be examined. Furthermore, the main effect of each outcome will be examined in the mixed effect model. Low correlated outcomes or outcomes that are highly (greater than .8) correlated with each other and/or low contribution in the model will be considered to be dropped from the model. The effect of mediators in the model can be calculated based on either the difference between two regression parameters ($\tau - \tau^2$) or the multiplication of two regression parameters ($\alpha\beta$) (MacKinnon, Warsi, & Dwyer, 1995). The variance estimates produced by the various methods are quite similar to each other and to the true value of the variance in situations involving continuous multivariate normal data and a continuous independent variable (MacKinnon et al., 1995). Although there is some evidence that the least model in the case-control study design setting this approach could provide biased estimations for the indirect effects (Wang et al., 2012), we believe the Sobel (1982) procedure to test for significant mediation is most appropriate approach for this study. Next we will use the formula provided by MacKinnon and Dwyer (1993) to determine the percentage of the intervention condition to primary outcome path that was accounted for by change in our mediator. We acknowledge that this method may not be supportable given the need to reduce sample size. If the study biostatistician determines that this is the case, she will utilize other strategies to analyze available data and generate testable hypotheses for future studies. The exploratory aim will be analyzed using similar approach. Data will be analyzed from all randomized subjects on whom we have a baseline assessment and at least one post-baseline evaluation. All statistical tests will be two-tailed. We will adjust p-values for multiple testing as appropriate.

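### The mediation plan has no check for a shared cause of change in mediator and CAPS, so a mediator that yoga moves could be reported as a mechanism when it is not one

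*Combined protocol and SAP*

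**What the plan says.** The Analytic Plan lists four conditions for mediation:

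- (a) an effect of treatment on CAPS
- (b) "a significant relationship between the independent variable and the proposed mediator"
- (c) "a significant relationship between the mediators and the outcome"
- (d) "the relationship between the independent variable and outcome must be significantly lower after controlling for the proposed mediator"

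On the test it says "we believe the Sobel (1982) procedure to test for significant mediation is most appropriate approach for this study". It then reports the percentage of the treatment effect carried by the mediator. In the two-mediator models one mediator is allowed to "causally affect the other mediator".

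The mixed model contains arm, time, their interaction and random effects. The one rule for adding covariates concerns differences between drop-outs and completers. Two caveats are attached to the mediation method: possible bias in case-control designs, and a fallback if the reduced sample cannot support it. Neither concerns confounding.

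Table 1 schedules every mediator at baseline, post-treatment and follow-up, the same visits as CAPS-5. Depression (CESD-R), anxiety, anger, insomnia and disability are also measured at those visits, but are assigned to Aim 1b only.

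**The concern.** Only treatment is randomised. Conditions (a) and (b) are therefore randomised contrasts. Condition (c), condition (d) and the beta in the Sobel product all depend on an observational association between change in the mediator and change in CAPS. A third factor that changes during the study and moves both will create that association with no causal path between them. Entering the mediator as change, or adjusting for its baseline value, does not remove a cause that itself changes. The link between the two mediators in the serial models is likewise not randomised.

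General distress is a natural candidate, and the section on the Coping model shows that the authors had it in mind. The rumination scale is described as having "strong correlations with measures of depression, anxiety and repetitive thought", and another avoidance scale was passed over because it is "highly reflective of general distress".

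Mechanisms are the secondary aim, and the Background states the hope plainly: "we believe that we will be able to identify pathways to change". The results are meant to inform practice guidelines and possible tailoring of yoga classes. As the plan stands, nothing it reports would show how easily a claimed mechanism could be explained by a shared cause.

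**Working it through.** The documents give no power, effect size or error rate for the mediation aim, so there is no figure of the plan's own to reproduce. The check asks how often the stated rule is met when the mediator has no effect on CAPS.

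**Inputs from the documents.** 48 per arm (Feasibility; Sample size). Attrition of 20%, the higher of the two rates considered, leaves 48 × 0.80 = 38.4, taken as 38 per arm. The arm effect on CAPS is 0.5 SD, the medium effect in Sample size. Tests are two-sided.

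**Assumed, not in the documents.** The .05 level for the mediation tests; an arm effect on the mediator of 0.5 or 0.8 SD; and a shared cause, not itself moved by yoga, giving a residual correlation r of .2, .3, .4 or .5 between change in mediator and change in CAPS.

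**Model.** Mediator change = α × arm + shared part + noise. CAPS change = τ × arm + shared part (opposite sign) + noise. There is no mediator term in the CAPS equation. α comes from the mediator on arm, and β from CAPS on mediator and arm. Sobel z = αβ / √(α²·se(β)² + β²·se(α)²), used here for condition (d).

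**Each condition alone, by approximation:**

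- (a): 0.5 × √(38/2) = 2.18 against a critical value of 1.99, so power is about 57%.
- (b): the same 57% at 0.5 SD. At 0.8 SD, 0.8 × √19 = 3.49, about 93%.
- (c): atanh(r) × √72 = 1.72, 2.63, 3.59 and 4.66 against 1.96, so it is falsely met in about 41%, 75%, 95% and over 99%.

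**All conditions together, by simulation:**

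| Arm effect on mediator | r = 0 | .2 | .3 | .4 | .5 |
|---|---|---|---|---|---|
| 0.5 SD, all four met | about 0% | 6% | 16% | 27% | 36% |
| 0.8 SD, all four met | about 1% | 14% | 32% | 49% | 55% |

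A repeat run with 20,000 trials per cell agreed within about one percentage point. A mechanism can be claimed only when (a) is met. Dividing by 57% gives about 11/28/47/63% and 25/56/86/96% of such trials.

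**False percentage mediated.** With unit residual variances β tends to −r, so the reported share tends to r × α/τ in absolute value. At α = τ = 0.5 this is 20/30/40/50%. At α = 0.8 it is 1.6 × r, or 32/48/64/80%.

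**Mediator that yoga does not move.** In a separate simulation at 38 per arm (0.65 SD arm effect on CAPS, mediator and CAPS loading .5/.7/.85 on the shared cause), all four conditions were met in 0.6/2.4/3.0% of trials. Condition (b) stops it.

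**Adjusting for measured distress.** At 48 per arm, with separate 0.65 SD arm effects on mediator and CAPS and the same loadings, the false rate is 38/78/82% unadjusted. It is 2/8/40% after adjusting for distress measured with reliability 0.9, and 4/21/78% with reliability 0.8. Adjustment helps but does not settle the question.

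**What a rho analysis would show.** In the linear model the residual correlation that brings the point estimate to zero equals the arm-adjusted mediator–CAPS correlation. With 76 participants (73 df), condition (c) needs |r| ≥ 1.99/√(1.99² + 73) ≈ .23. Every effect that passes (c) therefore has a point-estimate rho of at least about .23, and the rho for the confidence limit is the more informative figure.

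**The case against.** A reader might infer that any mediator improving alongside CAPS would be reported as a mechanism. The documents do not support that. Condition (b) requires the mediator to differ between arms, and a mediator that yoga does not move almost never passes. Condition (a) also fails in about 43% of trials under the assumed CAPS effect.

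A reader might also quote the rate at which Sobel alone is significant: about 9/24/39/51% at a 0.5 SD mediator effect and 24/52/78/89% at 0.8 SD. That is not the plan's rule, which requires all four conditions, and it overstates the risk. The plan also promises multiplicity adjustment as appropriate, which would lower the rates further.

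Nor do the documents show that the mediators are stand-ins for distress. The sentence on the rumination scale also reports that it is separable from mood. The chosen avoidance scale is said to relate more to avoidance than to negative affect, and the mindfulness scale is said not to track psychopathology closely. Digit Span is a performance test. These choices may well reduce the overlap, and correlations of .4 to .5 have no basis in the documents. No comparable reassurance about distress is given for the Distress Tolerance Scale, however, and choosing a measure does not test whether it changes together with CAPS.

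Finally, this is a general limit of mediation analysis in randomised trials, it touches a secondary aim, and the plan admits that the method may prove unworkable at this sample size. All of that is fair. But the admission is triggered by sample size, not by confounding, so it would not prompt the missing check.

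**Conclusion.** The concern holds in a bounded form. The mediator-to-CAPS path is observational, and the Analytic Plan contains no adjustment, stated assumption or sensitivity analysis for it. A mediator that yoga moves, and that shares a cause of change with CAPS, could be declared a mechanism when it is not one.

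The rates of about 6-36% and 14-55% depend on the assumed residual correlations and mediator effects, on change-score regression in place of the mixed model, and on no multiplicity adjustment. If the real overlap is near the low end and yoga's effect on the mediator is modest, the risk is small. The qualitative conclusion does not depend on those values: the rule cannot tell a mechanism from a marker that improves with CAPS for another reason. The change should be made because it costs little. Aim 1 is not affected.

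**What to change.** Add to the mediation text of the Analytic Plan:

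*The mediator-to-CAPS path is not protected by randomisation. Each indirect effect and percentage mediated is conditional on no unmeasured confounding of mediator and outcome. For each one we will report the residual correlation (rho) between the mediator and CAPS equations at which the estimate, and its confidence limit, reach zero. Effects nullified by a small rho will be described as associations.*

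What counts as small should be fixed before the data are analysed. It should be applied to the confidence limit, or set above about .23 if applied to the point estimate, since a lower cut-off would never be reached by an effect that passes condition (c) with 76 participants.

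As a descriptive supplement only, report each indirect effect with and without same-visit CESD-R. It should not decide between mechanism and association. Depression is measured after randomisation and may itself lie on the path, so adjustment could remove a real effect, and imperfect measurement could leave a false one.

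The cost is a paragraph of wording and a short extra analysis of data already scheduled in Table 1. The downside is that some Aim 2 results will be worded more cautiously.

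### Mediator indicators may be dropped for weak contribution in a model fitted to the same data that then test mediation, with no safeguard against the selection

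*Combined protocol and SAP*

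**What the plan says.** The mediation part of the Analytic Plan treats attentional control, tolerance of discomfort and coping as constructs measured by more than one instrument. It introduces the screening step as follows: "The relation among these variables and their individual contribution to the construct of interest will be examined in order to" "remove variables or create composites". Two looks at the data are then described. The first is at correlations among the indicators of a mediator. The second is an addition to it: "the main effect of each outcome will be examined in the mixed effect model". The consequence is stated next: "Low correlated outcomes or outcomes that are highly (greater than .8) correlated with each other and/or low contribution in the model will be considered" for removal. The last criterion, with the end of that sentence, reads: "low contribution in the model will be considered to be dropped from the model".

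Only the .8 correlation has a cut-off. No rule says when to drop an indicator and when to combine it with others.

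The mediation test uses the same data. "In this approach, four conditions must be met", among them (b), a significant treatment-mediator relationship, and "c) a significant relationship between the mediators and the outcome". On the test itself the plan states: "we believe the Sobel (1982) procedure to test for significant mediation is most appropriate approach for this study". The percentage of the treatment effect accounted for by the mediator is calculated afterwards.

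No alpha is given for Aim 2. The plan promises p-value adjustment where appropriate, without naming a method or a family of tests.

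**The concern.** Choosing indicators by how strongly they relate to something, and then testing that same relation in the same participants, makes the p-value of the retained indicators too small and pushes the estimate away from zero. The plan describes no split sample, no blinding to CAPS or allocation during screening, and no inference that allows for the selection.

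Which path is exposed depends on what contribution in the model means:

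- **Link with CAPS:** the mediator-outcome path, condition (c), is exposed.
- **Effect of treatment on the indicator:** the treatment-mediator path, condition (b), is exposed.
- **Contribution to the construct only:** neither is exposed.

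The protocol intends the mechanisms it identifies to shape guidance on how yoga is taught to Veterans. A path that looks supported because its indicators were picked for it would carry into that guidance.

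**Working it through.** The plan gives no sample size, power or error rate for Aim 2, so there is no stated figure to reproduce. The check asks what the screening rule does when the path being tested is truly zero.

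**Inputs**

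| Input | Value | Source |
|---|---|---|
| Randomised | 96 (48 per arm) | Sample size paragraph |
| Analysed | 96 × 0.80 = 76.8, about 77 | Upper of the plan's two attrition rates (10%, 20%) |
| Coping indicators | RTSQ, ERQ, BEAQ: k = 3, or 4 if both ERQ subscales count | Coping model section |
| Attentional control | Digit Span only in Table 1: k = 1, or 3 if subtests are used separately | Attention model section, Table 1 |
| Tolerance of discomfort | DTS only: k = 1 | Coping model section, Table 1 |
| Alpha | .05 two-sided | Assumed for Aim 2; two-sided is stated |
| Inter-indicator correlation | 0 to .7 | Assumed |
| Cut-off for low contribution | Several rules tried | Assumed |

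**Step 1, rough bound.** For k independent tests, the chance that at least one is falsely significant is 1 − (1 − .05)^k. For k = 3 this is 1 − .857 = 14.3%; for k = 4 it is 1 − .815 = 18.5%; for k = 1 it is 5%.

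**Step 2, selection on the link with CAPS.** CAPS was regressed on arm and the retained indicator or composite, with the true mediator-CAPS path set to zero. This simplifies the mixed model to a single time point. With 4,000 to 5,000 simulated trials per cell, the standard error at a 5% rate is about √(.05 × .95 / 4,000) = 0.3 points.

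| Rule | False-positive rate, mediator-CAPS path |
|---|---|
| Drop only the weakest (N = 77, k = 3-4, r = .2-.6) | 8-11% |
| Keep the best (N = 77, same k and r) | 12-14% (k = 3), 15-18% (k = 4); up to 19% in a smaller repeat run |
| Keep those with p < .2 (N = 77, same k and r) | 13-15% (k = 3), 15-21% (k = 4) |
| Keep the best (N = 96, r = 0-.7) | 11-14% (k = 3), 13-18% (k = 4) |
| Composite of all, fixed in advance (N = 77) | about 5% |
| Fixed indicator, fixed composite, joint test, or correlation-only screening (N = 96) | 4-6% |

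Dropping the weakest and keeping the best together span roughly 8-19%, or 8/5 = 1.6 to 19/5 = 3.8 times nominal. Backward elimination in which any surviving indicator may be significant gave 14-28% for k = 3-4 at N = 96. That also counts several uncorrected tests, so it is left out of the headline range.

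**Step 3, selection on response to treatment.** Keeping the indicator with the largest treatment effect (N = 77, k = 3-4, r = .2 and .6) leaves the mediator-CAPS path at 4-6%. The treatment-mediator path rises to 11-19% when treatment affects no indicator.

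**Step 4, the complete claim.** All four conditions plus Sobel, best indicator kept, true mediator-CAPS path zero, N = 96:

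| Treatment shift in mediator / CAPS | No selection | With selection |
|---|---|---|
| 0.5 / 0.5 SD | 0.3-0.8% | 1-2% |
| 0.8 / 0.8 SD | 2-3% | 5-8% |
| 1.2 / 0.8 SD | about 4% | 10-12% |

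Sobel alone after selection rejects in 1-4% at 0.5 SD shifts.

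**Step 5, estimates.** Later conditions do not undo selection in the estimate. An indicator kept because its sample association with CAPS was large has an exaggerated coefficient on average, and the percentage mediated is built on it. The direction follows from the selection; its size was not computed.

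**The case against.** The strongest defence has four parts.

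- **Dropping is discretionary.** The wording is only that dropping will be considered. This stands as a description, but an unspecified discretion exercised after seeing the data adds flexibility and protects nothing.
- **The step may be pure measurement.** It opens with contribution to the construct, and the coping section speaks of a latent variable from a set of indicators. This reading is possible, and on it there is no inflation. It leaves the added look at main effects in the mixed model unexplained, though. The mixed model the plan specifies has group and group-by-time effects, so response to treatment is also a natural reading.
- **Four conditions plus Sobel are conservative.** This stands at 0.5 SD. It does not settle the matter, because the Pilot Effect Sizes section says the study is powered for a medium to large effect, and at 0.8 SD shifts (an assumed large effect) the rate with selection is 5-8%.
- **Aim 2 is secondary, with p-value adjustment promised and a fallback to hypothesis-generating work.** The fallback applies only if the biostatistician invokes it, and the adjustment sentence does not address selection.

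A reader might also infer that selection favours the Coping Model over the Attention Model. The documents do not establish this. Only one of the Coping Model's two mediators has several instruments, Digit Span offers three separately scored subtests that could be screened in the same way, and no model comparison was simulated.

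**Conclusion.** The concern holds in conditional form. The plan permits removal of indicators on a criterion that may use CAPS or allocation, then tests on the same data without a safeguard. For a construct with 3-4 indicators, the path used for selection can have a false-positive rate of roughly 8-19% (CAPS-based) or 11-19% (treatment-based) in place of 5%. These figures rest on assumed k, correlation, dropping rule and alpha. They apply to coping and possibly to the Digit Span subtests; the DTS leaves nothing to select.

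Two stronger readings are tempting and should not be drawn. One is a fixed two- to four-fold inflation: the multiplier varies with the rule, starts at 1.6, and is 1 if screening ignores CAPS and allocation. The other is that p-values for the indirect effect are generally too small. At 0.5 SD shifts the complete conclusion is falsely reached in about 1-2%. Selection raises that rate relative to no selection, but the rate reaches or exceeds 5% only with larger shifts. What remains at any effect size, if selection uses CAPS, is upward bias in the selected path and in the percentage mediated.

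**What to change.** Delete the model-contribution criterion for dropping indicators. Define the maladaptive coping mediator in advance as a composite, for example the mean z-score of RTSQ, ERQ expressive suppression and BEAQ, and state whether ERQ reappraisal is used. Decide any dropping only from baseline inter-indicator correlations pooled over arms, with a stated cut-off for low as well as for high correlation, before anyone deciding sees CAPS or allocation. Apply the same rule to Digit Span: either one named score or a fixed composite of the subtests.

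The change fits the plan, which already foresees composites and a latent coping variable, and on the 2022 timeline the analyses were still ahead. It costs SAP wording. The downside is that a weak indicator may stay in the composite and dilute it somewhat.

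### Aim 2 tests a three-path serial mediation with the Sobel procedure, which is very conservative for small to moderate paths; a Monte Carlo interval should replace it before data lock

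*Combined protocol and SAP*

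**What the plan says.** Background and Significance sets out two chains, each ending in PTSD symptoms: yoga to mindfulness to attentional control (Attention model), and yoga to tolerance of discomfort to coping (Coping model). The Analytic Plan repeats the structure: "The multiple-mediation model includes a multiple-path mediating effect through both mediators".

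The same section then sets prerequisites: "In this approach, four conditions must be met: a) a significant relationship between the independent variable (treatment) and the dependent variable". Condition (b) is "a significant relationship between the independent variable and the proposed mediator (Attention Model: mindfulness and attentional control; Coping Model: tolerance of discomfort and coping". Condition (c) links mediators to outcome, and condition (d) is that "the relationship between the independent variable and outcome must be significantly lower after controlling for the proposed mediator".

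For the size of the mediated effect, the plan offers a difference of two parameters or "the multiplication of two regression parameters". For the test it says "we believe the Sobel (1982) procedure to test for significant mediation is most appropriate approach for this study". It adds a caveat, "We acknowledge that this method may not be supportable given the need to reduce sample size", and says that if the biostatistician agrees, "she will utilize other strategies to analyze available data and generate testable hypotheses for future studies".

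No alpha is given for Aim 2, only a general promise to adjust p-values as appropriate. The Sample size section covers Aim 1 only.

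**The concern.** Read literally, a two-coefficient product tests neither serial hypothesis. The natural extension, a Sobel test of the three-coefficient product, refers the estimate to a normal distribution. With three modest paths the product is skewed and far from normal, so the test rejects much too rarely. The conditions come on top. In a chain with no direct treatment path to mediator 2, the treatment effect on mediator 2 is itself a product, so a strict reading of (b) can veto a real serial effect.

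Aim 2 is a secondary aim, but the Innovation paragraph presents the comparison of the two models as the trial's main novelty, and the Intervention section would tailor yoga practice to the mechanisms found. A real mechanism of moderate size could well be reported as no mediation. The caveat does not settle this: it has no trigger and no named alternative, so the method could be chosen after the data are seen.

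**Working it through.** **The plan's own figure.** There is none for Aim 2. The only stated power is a minimum of 80% for Aim 1, so there is nothing to reproduce here.

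**Inputs from the documents.** 96 participants, 48 per group (Feasibility); two-tailed tests (Analytic Plan); 20% attrition as one planning value (Sample size), so 96 × 0.8 ≈ 77.

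**Assumed inputs.** Two-sided .05; path a (treatment to mediator 1) .5–.8 SD; paths d (mediator 1 to 2) and b (mediator 2 to CAPS) .3–.5; direct effect on CAPS .4; 1:1 allocation; unit residual SDs; one time point, ordinary least squares, no baseline adjustment.

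**Step 1: algebra, no path sizes needed.** The first-order Sobel statistic for three paths satisfies 1/z² = 1/t₁² + 1/t₂² + 1/t₃². With equal t, z = t/√3.
- t = 3 gives z = 3/1.732 = 1.73, p = .083.
- z = 1.96 needs t = 1.96 × 1.732 = 3.39 on every path (two paths: 1.96 × 1.414 = 2.77).

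**Step 2: the test alone.** Simulated power, Sobel against a 95% Monte Carlo interval for a·d·b:

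| a / d / b | N = 96 | N = 77 |
|---|---|---|
| .5/.3/.3 | 7% vs 41% | 3% vs 25% |
| .5/.39/.39 | 24% vs 61% | 11% vs 45% |
| .8/.3/.3 | 23% vs 61% | 10% vs 43% |
| .5/.5/.5 | 48% vs 69% | 30% vs 57% |
| .8/.39/.39 | 60% vs 89% | 34% vs 73% |
| .8/.5/.5 | 88% vs 97% | 69% vs 90% |

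With baselines as covariates at correlation .8, .5/.39/.39 gives 59% vs 88%. For single-mediator (two-path) products the gap is 2–20 points. With one path null at N = 96, Sobel rejects in about 0.1–1.6% of trials and the interval in about 2–5%.

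**Step 3: alpha.** At .01, the level the plan uses for hypothesis 1b, .5/.39/.39 gives about 1% for Sobel and 31% for the interval.

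**Step 4: condition (b) on mediator 2.** With no direct treatment path to mediator 2, its standardised treatment effect is a·d/√(1 + d²). For .5 and .39 this is .195/1.073 = .182 SD: power 14% at 48 per arm, and 476 per arm needed for 80%.

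**Step 5: adding (a) and (b)**, at .5/.39/.39, N = 96, .05:

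| Setting | Sobel + (a),(b) | Interval + (a),(b) |
|---|---|---|
| No direct effect on CAPS (total .5 × .39 × .39 = .076) | about 1% | about 1% |
| Direct effect .4, no direct path to mediator 2 | 4% | 9% |
| Direct effect .4, (b) on mediator 1 only | 15% | 36% |
| Direct effect .4, direct path of .3–.5 SD to mediator 2 | 16–20% | 35–49% |

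Conditions (c) and (d) are not modelled in this table; adding them cannot raise power.

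**The case against.** **The prerequisites may cost less than a strictly serial reading suggests.** This stands. The Coping model text says yoga may act directly on maladaptive coping, which is mediator 2; the figures are not visible; and (b) speaks of the mediator in the singular before listing both. A reader might therefore infer too much from setting 4% against 61%. That compares a test with prerequisites to one without, and the 4% needs a direct effect of .4, no direct treatment path to mediator 2, and both mediators required under (b). Matched pairs are 24% vs 61% without the conditions and 4% vs 9% with them. Nor can one say in general that replacing Sobel while keeping (a) and (b) gains little: on the last two rows of the table it more than doubles power.

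**Requiring a treatment effect first is defensible.** This stands in part. The protocol asks whether changes in the mediators explain clinical benefits that are observed. With a direct effect of .4, the serial part is .076 of .476, or 16%. Dropping (a) is partly a matter of preference.

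**The plan already concedes the weakness.** It does, and it labels the fallback as hypothesis-generating. It gives no criterion and no method, so the gap remains.

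**Multiplicity.** Adjustment lowers the interval's power too (Step 3). The ordering holds, but 61% should not be promised.

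**Allocation.** Procedures ties the original 2:1 ratio to Aim 2 power, so a reader might infer that reversing it cost power. The reversal aims at 48 per cell, and 2:1 at N = 96 does slightly worse (21% vs 58%). The loss comes from the smaller sample.

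**Conclusion.** The concern holds in this form. The plan poses three-path effects, writes no three-path test, and names a procedure that is very conservative for small to moderate paths and nearly adequate only for large ones. The algebra in Step 1 needs only the three-path extension and the .05 level. The power gap is 37 points at .5/.39/.39 (24% vs 61%) and 9 points at .8/.5/.5 (88% vs 97%), and the interval's null rejection stays near or below 5%.

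The prerequisites lower power further, but no single figure is supported: at .5/.39/.39, Sobel with (a) and (b) ranges from about 1% to 20%, and the interval with the same conditions from about 1% to 49%. The firm conclusions are that Sobel should be replaced and that a non-significant treatment effect on mediator 2 should not veto the serial effect. Path sizes, direct effects and the Aim 2 alpha are all assumptions, and single-time-point models stand in for the plan's mixed models. This is a should-change for a secondary aim and does not touch the primary analysis.

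**What to change.** Before data lock, amend the Aim 2 part of the Analytic Plan as follows.

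- Write out each three-path product and each single-mediator product, and name a Monte Carlo (distribution-of-product) interval as the criterion for mediation. This replaces both Sobel and the unnamed fallback.
- Use a percentile bootstrap as sensitivity analysis. It is placed second because its null rejection was 5.4–6.2% in the three settings tried.
- State the Aim 2 alpha after any multiplicity adjustment and set the interval level to match.
- Do not require a significant treatment effect on mediator 2 for the serial effect. Report conditions (a)–(d) alongside the interval.
- If the total effect on CAPS is not significant, report the indirect effect as hypothesis-generating, not as evidence of efficacy, and omit percent mediated.

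The cost is SAP wording and a short calculation from the fitted path estimates and their standard errors or covariances; no new data are needed. There are two downsides. Null rejection rises from under 2% to about 2–5%, and an indirect effect can be reported without a significant total effect, which is why its wording must be fixed in advance. The planned model-fit comparisons are unaffected.
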